Protocol and statistical plan

Validity and Reliability of the 6-minute Walk Test Over a Distance of 6 Metres in People With Multiple Sclerosis

NCT number: 04228328

10 January 2020

Protocol and statistical plan

Sponsor / Sponsor-Investigator	Pr [name], Professeur HES associé, [name], t : [contact], [contact]
Study Title	Validity and Reliability of the 6-minute Walk Test Over a Distance of 6 Metres in People With Multiple Sclerosis
Short Title / Study ID	VTM6M6m, CERVD-2019-01864
Study Registration	Clinicaltrial.gov : NCT04228328 Swiss National Clinical Trial Portal : SNCTP000003657
Study Category and Rationale	
Minimum risks (A category)
 
The tests are current and usual tests in the normal care of people with multiple sclerosis. Participants only have to walk for 6 minutes and to turn around. This turn will be timed.

Background and Rationale	The 6-minute walk test is used by physiotherapists to monitor the walking endurance of patients with multiple sclerosis. The protocol for this test calls for a distance of 30 meters (6MWT30) to be walked. However, this distance is not always available in practices and at patients' homes. The aim of this study is to validate a shorter version over a distance of 6 meters (6MWT6) and to evaluate its intra-rater reliability and the reliability of the instrument.
Risk / Benefit Assessment	
The risks are a temporary increase in fatigue and the risk of falling.
 
The direct benefits go beyond the knowledge of the performance of the tests. The participants will have feedback on their walking abilities and will use these data for their physiotherapeutic follow-up. Performing the tests will contribute to their training in walking and physical activity recommended in their situation.
 
The indirect benefits are the satisfaction of being able to help research on the disease that impacts them directly. Indeed, if there is a good correlation and concordance between the 6MWT6 and the 6MWT30, the use of the 6-minute test over 6 meters could be generalized.

Objective(s)	
The main objective is to validate a different version of the 6MWT, the 6MWT6.
 
The secondary objectives are to verify the reliability of this new version (of the instrument and of the rater) and to analyze the possible differences between the 6MWT6 and the 6MWT30 (according to the speed at the half-turn and other parameters: age, gender, height, EDSS score, type of disease, time since last relapse)

Endpoint(s)	
6-minute walk test over 6 meters: meters walked
 
6-minute walk test over 30 meters: meters walked
 
360 Degree Turn Test: time in seconds and number of steps

Study Design	Non-randomized validation study
Statistical Considerations	The primary objective is to validate a new version of the 6MWT over a distance of 6 m, so it is necessary to prove that there is an excellent correlation with the 6MWT30, the current reference. To do this, the data will be first presented, as means and standard deviations for normally distributed variables, and as medians and interquartile ranges for non-normally distributed variables. The differences between the 6MWT6 and 6MWT30 will be

	
plotted (absolute and relative values) and a test of comparison of means will be performed with Student's ttest.
 
Than, a Pearson or Kendall coefficient (depending on the distribution of the data) will be used. Analysis of the degree of agreement according to the method described by Taffé (bias and precision plot) will supplement the Bland and Altmann plot (Taffé, 2018; Taffé et al., 2020).
 
The secondary objective, reliability, will be assessed using the Intra Class Coefficient (ICC), according to the model: two-way mixed-effects as recommended by Koo (2016), as repeated measures cannot be considered as random sampling and absolute agreement, as agreement between repeated measures is sought (Koo & Li, 2016). The 6MWT6 data at Day1 will be compared to the same data at Day2 to assess intrarater reliability. These data will be compared to the post hoc count based on the video performed at Day1 and Day2 for instrument reliability.
 
For the last objective, analysis of explanatory factors for the differences between 6MWT6 and 6MWT30, correlation analyses will be performed between the continuous variable of these differences and the 360DTT. Multiple linear regressions will then be performed between this dependent variable "6MWT30 - 6MWT6" and the continuous and categorical variables: 360 DTT (time), age, gender, height, time since last relapse, type of MS, and assistive device. All analyses will be performed using STATA software, v.15.1. (StataCorp LLC, College Station, TX, USA).

Inclusion- / Exclusion Criteria	
The project focuses on the population of walking patients with MS.
 
Inclusion: adults, confirmed diagnosis of MS, Expanded Disability Status Scale (EDSS) score 3 to 6.5, or be able to walk 30 metres with or without aids, good understanding of French, have already completed a 6-minute walking test, be able to give consent by signature.
 
Exclusion: Lung disease, heart disease, co-morbidity preventing 6minWT, relapse in the last 3 months, chronic fatigue \geq at 8 (Visual Analog Score-Fatigue).

Number of Participants with Rationale	21 participants will be needed to obtain a good correlation coefficient, which is the objective of the validation of the new version of the 6MWT. The alpha was set at 0.01, the power at 0.9 for a correlation of 0.8
Study Intervention	Test under study: People have to walk for 6 minutes without stopping when possible.
Control Intervention	No control intervention.
Study procedures	Eligible patients will be recruited by their treating physiotherapist or through the presentation of the project to the regional groups of the Swiss MS Society. The patients will be interns at the Institution or will come to the Institution of Lavigny for 2 times 1 hour and 20 minutes of testing at one week intervals. On the first day (Day1), they will perform the 6MWT6, followed by a 15-45 minutes lying down break, then they will perform the 360 Degree Turn Test. On the second day (Day2), they will perform the 6MWT30 and then the 6MWT6, interspersed with a 15-45 minutes break.
Study Duration and Schedule	March to November 2020
Investigator(s)	[name], physical therapist Bsc, student in Master of Sciences. 21 years of experience with multiple sclerosis patients
Study Center(s)	Insitution de Lavigny, [name] Tél. [name] Switzerland

Ethical consideration	
1. The results of this study would be generalized to the population of MS walkers with an EDSS between 3 and 6.5. They will allow the use of a valuable tool, the 6MWT6, in previously impossible contexts, i.e. in the practices and at patients' homes. Participants will benefit directly from feedback on their abilities, be able to compare these results to previous results and use this data for their physiotherapeutic follow-up. Performing the tests will contribute to their training in walking and in the physical activity recommended for their situation. The indirect benefits are the satisfaction of being able to help research on the disease that impacts them directly. The main risk is a temporary increase in fatigue.
 
2. The proposed methodology is ethical because, in order to evaluate the reliability and validity of a test, while excluding the fatigue bias, it would be necessary to call the patient 3 times at a few days interval. In this context, it was attempted to do it in 2 days rather than 3 and the impact of fatigue was minimized through the systematization of the breaks in lying position with adjustable duration according to the patient's condition.

GCP Statement	
This study will be conducted in compliance with the protocol, the current version of the Declaration of Helsinki, the ICH-GCP, the HRA as well as other locally relevant legal and regulatory requirements. A clinical trial covered by ClinO Chapter 4 may be conducted in accordance with other rules than ICH-GCP guidelines, provided that such rules are recognised in the specialty in question and the protection of participants and data quality and security are guaranteed (ClinO Art. 5, Abs 2). If the clinical trial is not conducted according to ICH-GCP guidelines, the paragraph above must be adapted accordingly.

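### Correlation is the only stated proof of the 6MWT6's validity and the only basis for the sample size; the planned agreement analyses have no acceptance limit and no stated role in the conclusion

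*Combined protocol and SAP*

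**What the plan says.** The combined protocol and SAP deals with validity in several places.

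- **Statistical Considerations, criterion.** For the primary objective, "it is necessary to prove that there is an excellent correlation with the 6MWT30". No numerical value defines excellent.
- **Statistical Considerations, methods.** The same entry plans plots of the absolute and relative differences, and "a test of comparison of means will be performed with Student's ttest". Next, "a Pearson or Kendall coefficient (depending on the distribution of the data) will be used". Agreement analysis follows: "bias and precision plot) will supplement the Bland and Altmann plot". No acceptable bias, acceptable limits of agreement or equivalence margin is given.
- **Number of Participants with Rationale.** This entry sizes the study on correlation: "21 participants will be needed to obtain a good correlation coefficient, which is the objective of the validation". The inputs are alpha 0.01, power 0.9 and a correlation of 0.8.
- **Risk / Benefit Assessment.** Wider use of the 6 m test is foreseen "if there is a good correlation and concordance between the 6MWT6 and the 6MWT30".
- **Ethical consideration.** Participants are expected to set their results beside earlier ones and to use them in physiotherapy follow-up.

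**The concern.** The document sets two standards. Risk / Benefit Assessment asks for correlation and concordance. Statistical Considerations attaches proof to correlation alone, and the sample-size entry calls a good correlation the objective of the validation. The analyses that address concordance are planned, but no result from them is defined as good enough or as too poor.

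This matters because the two properties can part company. A constant or proportional shortfall leaves r unchanged. The protocol itself anticipates a difference, since it plans to explain 6MWT30 − 6MWT6 by turning time and other factors. A 6 m course also requires 30/6 = 5 times as many turns per metre. If a 6 m result is to be read against an earlier 30 m result, or used to follow one patient, the relevant quantities are the bias and the spread of differences in metres. As written, a high r would satisfy the stated proof whatever those quantities turned out to be.

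**Working it through.** **1. The plan's own figure.** Inputs from Number of Participants with Rationale: alpha 0.01, power 0.9, r = 0.8. Sidedness and the null value are not stated, so I take the null as 0.

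Fisher z: n = [(z_α + z_power)/atanh(r)]² + 3, with atanh(0.8) = 1.0986.

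- Two-sided: [(2.576 + 1.282)/1.0986]² + 3 = 15.33, so 16.
- One-sided: [(2.326 + 1.282)/1.0986]² + 3 = 13.78, so 14.

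The stated 21 is not reproduced. It is reached only with inputs that the plan does not give, for example a non-zero null or a dropout allowance (16 inflated for 20–25% dropout gives 20–22). Low power is not the problem: 21 gives about 98% power two-sided against zero. No agreement quantity enters the calculation.

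**2. What a correlation at n = 21 establishes.** At two-sided alpha 0.01, any observed r above 0.549 differs significantly from zero. An observed r of 0.80 has a 95% CI of tanh(1.0986 ± 1.96/√18) = 0.56 to 0.92.

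**3. What a given r implies for agreement.** Assume equal SDs for the two tests. Then SD of differences (SDd) = SD × √(2(1 − r)), and the 95% limits are bias ± 1.96 × SDd.

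| r | SDd / SD | Limits around the bias |
|---|---|---|
| 0.80 | √0.40 = 0.632 | ±1.24 SD |
| 0.90 | √0.20 = 0.447 | ±0.88 SD |
| 0.95 | √0.10 = 0.316 | ±0.62 SD |

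The documents give no between-patient SD. For an assumed 80 to 120 m, r = 0.80 corresponds to ±99 to ±149 m and r = 0.95 to ±50 to ±74 m. The bias itself can take any value without changing r.

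**4. A high r with a shortfall (illustration, all inputs assumed).** Distance = 360·L/(L/v + c) for L = 30 or 6 m. Speed v has mean 0.95 and SD 0.28 m/s, time lost per turn c has mean 1 or 2 s (SD 0.3 or 0.6), and each test carries 3% random error.

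| Mean turn cost | r | Mean shortfall of 6MWT6 | 95% limits of 6MWT30 − 6MWT6 |
|---|---|---|---|
| 1 s | about 0.98 | about 38 m | about −12 to +88 m |
| 2 s | about 0.95 | about 63 m | about −6 to +133 m |

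As a check at the mean values with c = 1 s: 10800/(31.58 + 1) = 331.5 m against 2160/(6.32 + 1) = 295.3 m, a difference of about 36 m.

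**5. What the t-test adds.** In paired form at 0.05 with n = 21, it has 80% power only for a bias of about 0.64 SDd, and 59% power for 0.5 SDd. It describes bias; a non-significant result would not show that bias is absent.

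**6. Precision of agreement at n = 21.** With t(0.975, 20) = 2.086:

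- Mean difference: 2.086/√21 = 0.455 SDd.
- Each limit: 2.086 × √(1/21 + 1.96²/40) = 0.79 SDd.

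By the normal approximation, a half-width of 0.5 SDd for each limit would need 46 participants, and 0.4 SDd would need 71.

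**The case against.** The strongest reply is that agreement is already in the plan. After naming correlation, Statistical Considerations lists the whole set of analyses under the primary objective, and Risk / Benefit Assessment makes concordance a condition of wider use. A test that read far shorter would show up in the difference plots, the t-test and the Bland-Altman plot. This stands as far as it goes: the data and most of the methods are in place. It does not supply a standard by which those results would count for or against validity.

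Three stronger readings might be inferred, and the documents do not support them.

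- **Agreement is only a supplement to correlation.** The sentence says that the bias and precision method "will supplement the Bland and Altmann plot", so one agreement method supplements another.
- **The t-test is offered as proof of validity.** It is listed with the plots of differences, and nowhere is a non-significant result said to show agreement. Only correlation is tied to proof.
- **The EDSS range artificially inflates r.** EDSS 3 to 6.5 is the population to which the results are to be generalised, so sampling it is appropriate.

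It can also be said that the protocol never claims the two tests are interchangeable, that it expects a difference and sets out to explain it, and that participants could compare a new 30 m result with an old one. That is fair. It is a reason to define what validity will mean in metres, and to plan a conversion if a shortfall is found. It does not make correlation sufficient.

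**Conclusion.** The concern holds in this form: correlation is the only criterion tied to proof and the only basis for N. Concordance, which the protocol itself names as a condition for wider use, has no acceptance limit and no defined part in the conclusion. A high r would therefore meet the stated proof despite a large shortfall or wide limits.

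The size is ±1.24 SD at r = 0.80 and ±0.62 SD at r = 0.95, around whatever bias exists. These figures rest only on equal SDs and the usual normal limits. The metre values and the turning model are illustrations on assumed inputs and show what could happen, not what will. The point should be corrected before analysis. It does not mean that the wrong analyses are planned, since the relevant ones largely are.

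**What to change.** In Statistical Considerations:

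1. Make the primary validity result the paired mean difference 6MWT30 − 6MWT6 with its 95% CI, and the 95% limits of agreement with CIs. Use the already planned bias/precision model if the difference grows with distance.
2. Have the investigator fix a maximum acceptable difference in metres before data are seen, and judge the result against it. If it is exceeded, conclude that the tests are correlated but not interchangeable, and report an equation converting 6MWT6 to 6MWT30 with its prediction error.
3. Keep the correlation as supportive. State that the t-test is paired and report it only as a description of bias.
4. In Number of Participants with Rationale, say that N was not chosen for agreement, and give the expected precision at 21 (about 0.79 SDd for each limit).

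**Cost.** No new measurements are needed. The CIs for the limits and the conversion equation are small additions to the planned analysis. The conclusion may be less favourable. With 21 participants the limits will be imprecise, so a result close to the acceptable difference may be inconclusive.

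### Day 1/Day 2 repeatability of the 6MWT6 is planned only as a unitless ICC, so the plan gives no measurement error in metres although the walk test is described as a monitoring tool

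*Combined protocol and SAP*

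**What the plan says.** **Use of the test.** Background and Rationale says: "The 6-minute walk test is used by physiotherapists to monitor the walking endurance of patients with multiple sclerosis". Risk / Benefit Assessment adds: "The participants will have feedback on their walking abilities and will use these data for their physiotherapeutic follow-up". Ethical consideration says that participants will "be able to compare these results to previous results and use this data for their physiotherapeutic follow-up". The outcome under Endpoint(s) is in metres: "6-minute walk test over 6 meters: meters walked".

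**Reliability analysis.** Statistical Considerations says "The secondary objective, reliability, will be assessed using the Intra Class Coefficient (ICC", specified as two-way mixed-effects with absolute agreement. The comparison is defined as follows: "The 6MWT6 data at Day1 will be compared to the same data at Day2 to assess intrarater reliability". The section gives no SEM, minimal detectable change, repeatability coefficient or Day 1/Day 2 limits of agreement. It also gives no acceptance threshold or confidence interval for the ICC.

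**Agreement plots.** The plan does include agreement methods ("bias and precision plot) will supplement the Bland and Altmann plot"), but they stand in the part of the section that compares the 6MWT6 with the 6MWT30, before the reliability paragraph begins.

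**Design.** Under Study procedures the 6MWT6 is done on two days one week apart: first in the session on Day 1, and after the 6MWT30 and a rest on Day 2.

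**The concern.** A physiotherapist who compares a patient's distance today with an earlier one needs to know how large a difference can arise from measurement error and ordinary week-to-week variation. That figure is in metres. The ICC instead gives the share of total variance that is due to differences between patients. Entry is broad (EDSS 3 to 6.5, or able to walk 30 m, with or without aids), so those differences are likely to be large, and a high ICC can then coexist with a large error in the individual patient.

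At stake is what the reliability result can be used for. As planned, it would rank the 6MWT6 on a unitless scale but tell a user nothing direct about reading a change between two 6MWT6 results, even though both results per participant will be in the data set.

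**Working it through.** **Inputs from the documents.** n = 21 (Number of Participants with Rationale); two 6MWT6 results per participant (Study procedures); absolute-agreement ICC only (Statistical Considerations). No SD, expected ICC or clinically relevant change in metres is given.

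**The plan's own figure.** The reliability analysis has no figure to reproduce. The 21 participants were set for the correlation with the 6MWT30 (alpha 0.01, power 0.9, correlation 0.8). Fisher's z against a null of zero gives, two-sided, ((2.576 + 1.282) / 1.0986)² + 3 = 15.3, so 16; one-sided it gives 13.8, so 14. The stated 21 exceeds both. The point here does not depend on this; 21 simply fixes the information available for repeatability.

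**Formulas.** Let SD be the standard deviation across patients of a single 6MWT6 distance.

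- ICC = 1 − SEM² / SD², so SEM = SD × √(1 − ICC)
- MDC95 = 1.96 × √2 × SEM = 2.77 × SEM

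**Same error, different ICC.** Assume SEM = 30 m, so MDC95 = 1.96 × 1.414 × 30 = 83 m. The SDs are also assumptions.

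| Assumed SD (m) | ICC | MDC95 (m) |
|---|---|---|
| 60 | 1 − 900/3600 = 0.75 | 83 |
| 100 | 1 − 900/10000 = 0.91 | 83 |
| 150 | 1 − 900/22500 = 0.96 | 83 |

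The error facing the individual patient is identical in the three rows. Only the mix of patients changes.

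**In SD units.** MDC95 = 2.77 × SD × √(1 − ICC) is 0.88 SD at an ICC of 0.90 and 0.62 SD at 0.95. An ICC becomes a figure in metres only once the SD is known.

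**Precision with 21 participants.** Taking the SEM as the SD of the paired differences divided by √2 leaves 20 degrees of freedom. The chi-square interval multiplies the estimate by √(20/34.17) = 0.77 at the lower end and √(20/9.59) = 1.44 at the upper end. For the assumed MDC95 of 83 m, that is about 64 to 120 m. An observed ICC of 0.90 would itself have a 95% interval of about 0.77 to 0.96 (F method, consistency form, as an approximation).

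**The case against.** The case against has several parts.

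- **The objective is narrower than monitoring.** Objective(s) asks for reliability of the instrument and of the rater, and an ICC addresses that. The monitoring sentence in Background and Rationale describes the existing test. The remark about previous results is a participant benefit and may refer to earlier standard tests, since a prior six-minute walk is an entry condition. This stands in part: follow-up use is context, not a formal objective. It is still the reason the documents give for having the test.
- **The ICC is not blind to error.** Absolute agreement penalises a systematic Day 1/Day 2 shift, and a large error with modest spread lowers the ICC. This stands. A reader might infer that the ICC will be high almost whatever the error; the first row of the table, at 0.75, shows otherwise.
- **Readers could derive the SEM themselves.** With an SD and an ICC they could, approximately. However, the plan reports distances "as means and standard deviations for normally distributed variables, and as medians and interquartile ranges for non-normally distributed variables", so the SD may not appear, and no interval is planned in either case.
- **The bias and precision plot might show 6MWT6 precision in metres.** That depends on a cited method whose source is not available here. The plan does not assign it to the Day 1/Day 2 comparison.
- **The metre figures are assumptions.** They are. At a fixed ICC the MDC95 is simply proportional to SD, so a spread of MDC values would restate the assumed SD range. The table therefore fixes the error and lets the ICC vary.
- **An MDC from 21 people is imprecise.** True, which is a reason to report its interval rather than to omit it.

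**Conclusion.** The omission is real and of moderate weight. The plan specifies no repeatability figure in metres for the 6MWT6, and the ICC cannot stand in for one: under the assumed SDs of 60 to 150 m, one error of 30 m is compatible with ICCs from 0.75 to 0.96. That illustration rests on assumed SD and SEM values; the dependence of the ICC on patient spread does not.

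Two stronger readings are not supported. A reader might infer that the 6MWT6 cannot detect the changes clinicians need to see. The documents give no SD, no expected ICC and no clinically needed change, so they show only that the planned statistic would not reveal the detectable change. A reader might also infer that a high ICC would by itself lead to a recommendation for follow-up use. Risk / Benefit Assessment ties wider use to correlation and concordance with the 6MWT30, and no text makes it depend on the ICC.

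The point concerns a secondary objective. It leaves the primary comparison, the sample size and the data collection untouched.

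**What to change.** In the reliability paragraph of Statistical Considerations, keep the ICC and pre-specify the following from the Day 1 and Day 2 6MWT6 results:

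1. the mean Day 1/Day 2 difference with its 95% confidence interval;
2. the SEM (SD of the paired differences divided by √2) and the MDC95, each with a 95% confidence interval, in metres and as a percentage of the mean distance;
3. a Day 1/Day 2 Bland-Altman plot with limits of agreement.

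State that any sentence about follow-up use will cite these figures. It should also note that with 21 participants the interval runs from about 0.77 to 1.44 times the estimate, and that the error includes one week of patient variation and the Day 2 sequence, in which the 6MWT6 follows the 6MWT30.

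The cost is a few lines of text and a small extra analysis, with no added participants, visits or tests. The one drawback is that the result may look less favourable than an ICC alone.

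### Instrument reliability of the 6 m walk test rests on an ICC alone, which stays near 0.98 or higher when every walk is miscounted by two lengths

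*Combined protocol and SAP*

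**What the plan says.** The Objective(s) row of the combined protocol and SAP includes a secondary aim "to verify the reliability of this new version (of the instrument and of the rater"). The outcome is a distance: "6-minute walk test over 6 meters: meters walked".

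Under Statistical Considerations, reliability "will be assessed using the Intra Class Coefficient (ICC), according to the model: two-way mixed-effects", with "absolute agreement, as agreement between repeated measures is sought". Two comparisons come under that heading. The Day 1 and Day 2 6MWT6 results address the rater. For the instrument, the same results are set against the "post hoc count based on the video performed at Day1 and Day2 for instrument reliability".

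Difference-based agreement methods appear earlier in the same row, for 6MWT6 against 6MWT30, where the "bias and precision plot) will supplement the Bland and Altmann plot". They are not mentioned for live against video.

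The documents do not state an acceptable ICC, an error limit, whether the ICC is for single or average measures, who counts the video, or whether that person can see the live result.

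**The concern.** The live and video counts describe one and the same walk. Nothing about the participant changes between them, so their difference is counting error and nothing else. An ICC does not report that error in lengths or metres. It reports the share of total variance that lies between people. Here that share is large by design, because the trial admits people with EDSS 3 to 6.5, walking with or without aids.

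The number of lengths to be counted is one practical difference between the two courses: a 300 m walk is 300/6 = 50 lengths on the short course and 300/30 = 10 on the long one. The test is meant for practices and patients' homes, where a user needs to know how far a recorded distance may be off. If the ICC is the only result, the study could report excellent instrument reliability and leave that question unanswered.

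**Working it through.** **Inputs.** From the documents: 21 participants; one length is 6 m; two-way, absolute-agreement ICC. Assumed, because the documents give no figures: mean distance μ = 300 m, between-person SD S = 60 to 150 m, single-measure ICC, and the video count taken as the truth. The plan states no ICC, threshold or miscount rate, so there is no planned figure to reproduce.

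**Case A: every walk wrong by d metres.** If one of the two counts is off by d in every walk, either always low or with random sign, then approximately

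ICC = S² / (S² + d²/2).

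| S (m) | d = 6 m (one length) | d = 12 m (two lengths) |
|---|---|---|
| 60 | 3600/3618 = 0.995 | 3600/3672 = 0.980 |
| 100 | 10000/10018 = 0.998 | 10000/10072 = 0.993 |
| 150 | 22500/22518 = 0.999 | 22500/22572 = 0.997 |

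Simulation of the planned ICC with 21 walks agrees: the median at d = 12 m is about 0.98 for S = 60 m and 0.996 to 0.997 for S = 150 m. In all these rows no walk has matching counts.

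**What differences would show in Case A, d = 12 m.** If the live count is always two lengths short, the mean difference is −12 m (−2 lengths) and the proportion of identical counts is 0%. If the sign is random, the mean difference is about 0, the SD of differences is about 12 m, and the limits of agreement are about ±1.96 × 12 = ±23.5 m, or ±3.9 lengths. Either result is plain to a reader; an ICC of 0.98 or more is not.

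**Case B: each length missed independently with probability p.** The live count then averages (1 − p) times the true distance, with extra variance 6μp(1 − p), and is low by pμ on average. To a close approximation

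ICC = 2(1 − p)S² / [S² + (1 − p)²S² + 6μp(1 − p) + (pμ)²].

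For p = 0.10 and S = 60: 6480 / (3600 + 2916 + 162 + 900) = 6480/7578 = 0.855. For S = 150: 40500 / (22500 + 18225 + 162 + 900) = 40500/41787 = 0.969.

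| Lengths missed | Mean loss at 300 m | S = 60 | S = 100 | S = 150 |
|---|---|---|---|---|
| 2% | 6 m | 0.990 | 0.996 | 0.998 |
| 5% | 15 m | 0.955 | 0.983 | 0.991 |
| 10% | 30 m | 0.855 | 0.939 | 0.969 |
| 20% | 60 m | 0.588 | 0.789 | 0.883 |

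Simulated medians lie within about 0.01 of these. If errors go in both directions instead, miscounting 20% of lengths still leaves a simulated median of 0.953 (mean 300 m, S = 60) to 0.989 (mean 400 m, S = 150).

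**Sensitivity to the assumed SD.** Below 60 m the ICC drops: with S = 40 and d = 12, 1600/1672 = 0.957. If an average-measures ICC were used, the values would be higher than those shown.

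**The case against.** The strongest reply is that the planned ICC is of the right type. Because it is defined by absolute agreement, a systematic undercount lowers it, and Case B shows it falling well below 0.98 once some 10% of lengths are missed. This stands. A reader might infer that the ICC stays high however often lengths are miscounted; the plan's own definition of the ICC rules that out.

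A reader might also infer that the objective cannot fail. That does not follow either. No threshold is stated, so there is no pass or fail at all; the gap is an absent criterion together with a statistic that is weak for small errors.

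A third tempting inference is that the video count is unmasked and made by the person who counted live. The documents are silent on both. One person appears in the Investigator(s) row, but nothing identifies that person as the live or video counter, and the sponsor-investigator is a separate entry. Lack of independence is possible, not established.

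It can also be said that an error of 6 or 12 m may not matter clinically, so that a high ICC would be a fair description, and that the documents attribute differences between the courses to turning and patient factors, not to miscounting. This is fair: the documents do not show that miscounting is common or important. But whether 12 m matters is for the user to judge, and the user can do so only if the error is reported.

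**Conclusion.** The point holds in a limited form. For live against video the plan names only an absolute-agreement ICC. With an assumed between-person SD of 60 to 150 m, that ICC is about 0.98 to 0.996 when every walk is wrong by 12 m, and 0.995 or higher when every walk is wrong by 6 m. It does respond to accumulated undercounting (about 0.85 to 0.97 at 10% of lengths missed). It can therefore flag gross failure but cannot reveal errors of one or two lengths.

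The figures rest on an SD and mean that the documents do not give, on a single-measure ICC, and on the video count being correct. With an SD below 60 m the two-length figure drops below 0.98.

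Silence about who counts the video is a gap in description, secondary to the choice of statistic. The matter affects one part of a secondary objective, leaves the primary validation against the 6MWT30 untouched, and is a low-cost improvement, not a serious flaw.

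**What to change.** Extend to live versus video the agreement analysis already planned for 6MWT6 versus 6MWT30. For each 6MWT6, report:

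- the mean live-minus-video difference with limits of agreement, in lengths and in metres;
- the proportion of walks with identical counts;
- the largest discrepancy.

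Keep the ICC as a supportive figure and say whether it is for single or average measures. Each participant contributes a Day 1 and a Day 2 walk (2 × 21 = 42 pairs), so give the results by day, or allow for the pairing within person if the days are pooled. If the sponsor wants a verdict on the objective, state beforehand what size of error would be acceptable.

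State who counts the videos, and have them counted from coded files in shuffled order without access to the live count sheets. This does not mask fully, since a rater may recognise a participant on film, but it removes direct sight of the earlier figure.

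The recordings are already planned, so the cost is coding and shuffling files and a few sentences in the plan; no added participants, visits or staff are needed. The downside is slightly more file handling and possibly a less flattering result.
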